#### 6.2. Sample size estimation/power analysis:

Thirty-two patients will be needed in each group to find a 25-mm difference between the group means on the VAS at 60 min, with a power of 0.80 and an alpha of 0.05. We will aim for 35 patients per group to account for about a 10% dropout rate

# 6.3. Statistical Analysis:

The groups will be compared using a t-test on gender, race, and age; and a  $\chi^2$  test with Yates correction on severity of presenting headache, to determine if they are similar. The individual VAS measurements will be compared using a repeated measures analysis of variance (ANOVA) test.

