# **Screening Visit:**

- Obtain signed Informed Consent Document and HIPAA Authorization (research-driven).
- Record: Date of birth, age, phone number, gender, race, ethnicity, social security number, name of standard of care rescue medications (over-the-counter and prescription), current email address (to be used for scheduling only), height (in inches), weight (in pounds), history of traumatic brain injury, concussion, or any mild to severe head trauma, medication use. (research only)
- Review past medical history in Armed Forces Health Longitudinal Technology Application (AHLTA) or ESSENTRIS to verify the inclusion/exclusion criteria.
- Women of childbearing potential will have a serum pregnancy test (5-10 milliliters, approximately 1-2 teaspoons of blood) or urine pregnancy test (10 drops or less than 1 milliliter of urine) (research-driven).

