#### Visit 1:

- Heart rate
- Blood pressure
- Headache severity via 100-mm VAS.
- Nausea severity via 100-mm VAS.
- Vomiting severity via 100-mm VAS.
- Anxiety severity via 100-mm VAS.
- Restlessness severity via 100-mm VAS.
- Record type and amount of rescue medications (over-the-counter and prescription) use in the past 7 days.
   (research only)
- Subjects will be randomized by the pharmacy. We will use a random-number generator and use blocking to ensure roughly equal sample sizes. Both subjects and investigators will be blinded to the study group assignments. Subjects will be randomized by the pharmacy into one of two groups (research-driven):
  - Group 1: Standard treatment arm (compazine 10 mg IV along with diphenhydramine(Benadryl) 25 mg
     IV)
  - Group 2: Research arm (Ketamine 0.3 mg/kg along with ondansetron (Zofran) 4 mg IV)

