# 3.6.1. Interventions, Observations, or Data Sought:

The primary outcome measure will be the difference in pain scores between the compazine and Ketamine groups, measured as the absolute difference between the means at 60 min. Secondarily, we will measure the difference between the rates of decline in pain scores, rate of admission, nausea scores, rate of vomiting, rate of development of akathisia, heart rate and blood pressure changes, headache resolution with telephone follow up, and patient satisfaction.

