#### 6.o. Data Analysis:

A couple prior studies have used a 25-mm difference in mean VAS score reduction between groups to show a clinical benefit [6,9]. We define adequate pain relief as an absolute decrease in the mean VAS score of 25 mm [24, 25, 26, 27].

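### Section 6.3 plans a Yates chi-square on a severity score recorded only as a continuous VAS with no cut-point, and a t-test on race whose result depends on coding if race has three or more categories

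*Combined protocol and SAP*

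**What the plan says.** Section 6.3 describes two sets of analyses.

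- **Baseline.** "The groups will be compared using a t-test on gender, race, and age"; and a chi-square "test with Yates correction on severity of presenting headache, to determine if they are similar".
- **Outcome.** "The individual VAS measurements will be compared using a repeated measures analysis of variance (ANOVA) test".

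The variables are defined in section 3.6. The Screening Visit list includes "Date of birth, age, phone number, gender, race, ethnicity", with no categories or coding for race. Visit 1, before treatment, records "Headache severity via 100-mm VAS". The table in section 3.6.5 counts five such readings per patient (Visit 1, then 15, 30, 45 and 60 min).

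Sections 3.6.1 and 6.1 define the primary outcome as the difference in pain scores, "measured as the absolute difference between the means at 60 min". Section 6.0 justifies the target by earlier studies that used a "25-mm difference in mean VAS score reduction between groups". Section 6.2 sizes the trial: "Thirty-two patients will be needed in each group to find a 25-mm difference between the group means on the VAS at 60 min", with power 0.80 and alpha 0.05, raised to 35 per group for dropout.

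**The concern.** Two of the four baseline tests do not sit well with their variables.

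- **Severity.** The Yates correction belongs to a 2x2 table. A 0-100 mm score gives such a table only after it is split, and the plan does not say where. The analyst would choose the split later, and splitting discards information.
- **Race.** A t-test compares means. Nominal categories have a mean only after numbers are attached to them. With three or more categories, the p-value then depends on the numbering.

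The stated purpose is also unsound. After randomisation any baseline difference is due to chance, and a non-significant test in 70 patients does not show that the groups are alike.

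What is at stake is the interpretability of the baseline comparison. A separate, smaller matter is that section 6.3 does not say how the repeated measures ANOVA uses the pre-treatment VAS, although section 6.0 speaks of a reduction and section 6.1 of means at 60 min.

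**Working it through.** **1. Is there a severity cut-point anywhere?** The 25-mm figures in sections 3.2, 6.0 and 6.2 are between-group differences or decreases, not baseline categories. The 0-10 pain question is asked only at 24-48 hours. No section groups presenting severity.

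**2. How much does the cut matter?** Assumptions, since the documents give no baseline distribution: 35 per arm (section 6.2), no true difference, and VAS drawn from a normal distribution with mean 70 and SD 25, then clipped to 0-100 mm. The clipped data have mean 68.6 and SD 22.5. A Yates chi-square was run at each of four cuts.

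| Cut (mm) | Share of trials with p < 0.05 |
|---|---|
| 50 | 2.6% |
| 60 | 3.0% |
| 70 | 2.3% |
| 80 | 3.0% |

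The verdict differed between cuts in about 8% of trials. Each fixed cut is conservative; the difficulty is that the plan fixes none.

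The information lost shows when a real imbalance is imposed. With mean 70, SD 20 before clipping, 35 per arm and a 10-mm shift, a t-test on the VAS rejects in 54% of trials and the Yates chi-square in 22% to 29%, depending on the cut.

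**3. Race.** Hypothetical counts for three categories: 20/5/10 in one arm, 20/11/4 in the other.

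| Codes given to the three categories | Arm means | t-test p |
|---|---|---|
| 1, 2, 3 | 60/35 = 1.714 v 54/35 = 1.543 | 0.375 |
| 1, 3, 2 | 55/35 = 1.571 v 61/35 = 1.743 | 0.393 |
| 2, 1, 3 | 75/35 = 2.143 v 63/35 = 1.800 | 0.028 |

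The chi-square on 2 df is 4.82, p = 0.090, whatever the labels.

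**4. Gender and age.** The t-test suits age. For a two-level gender variable it nearly equals the uncorrected chi-square: hypothetical 22/35 v 13/35 gives 0.0316 against 0.0314.

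**5. Does anything depend on these tests?** The primary outcome (3.6.1, 6.1), the sample size (6.2) and the ANOVA (6.3) do not use them. No section ties inclusion, model choice or conclusions to them.

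**6. What adjustment for the pre-treatment VAS would gain.** Section 6.2 states no SD, so its 32 per group cannot be reproduced directly. Solving for the SD that gives power 0.80 for 25 mm at two-sided 0.05 (sidedness is not stated) with 32 per group yields 35.1 mm by noncentral t (35.7 mm by normal approximation).

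- Unadjusted 95% CI half-width = t(62 df) × SD × √(2/32) = 1.999 × 35.1 × 0.25. With the unrounded SD this is 17.6 mm.
- Adjusted half-width = the same, with t on 61 df, multiplied by √[(1 − ρ²)(1 + 1/60)]. Here ρ is the baseline-to-60-min correlation and 1/60 = 1/(64 − 4) is the cost of estimating the covariate.

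| Assumed ρ | Multiplier | Half-width (mm) |
|---|---|---|
| 0.3 | √(0.91 × 1.0167) = 0.962 | 16.9 |
| 0.5 | √(0.75 × 1.0167) = 0.873 | 15.3 |
| 0.7 | √(0.51 × 1.0167) = 0.720 | 12.6 |

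**The case against.** The strongest reply is that this is under-specification in a baseline table with no inferential consequence. Most of it stands, and it rules out several stronger readings.

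- *A reader might infer that the severity test cannot be run at all.* It can, once a cut is chosen. The fault is that none is stated and that a continuous score is split without need.
- *A reader might infer that the race test is certainly invalid.* Section 3.6 gives no categories. If race were recorded in two groups, the t-test would be nearly as harmless as it is for gender. The criticism is therefore conditional.
- *The two tests may simply have been swapped in drafting.* That is possible, but the documents do not say so, and a swapped sentence still needs correcting.
- *The simulation measures little that matters.* Its inputs are assumed, and nothing downstream uses the test. It shows only that the answer turns on an unstated choice. Nothing suggests that the investigators intend to try several cuts.
- *Baseline adjustment is a different topic.* It is, and it is kept apart here. Its size rests on a correlation that the documents do not give. Any treatment is permitted after 30 minutes, which may lower that correlation.

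The reply does not rescue the sentence itself: it names tests unsuited to the data as described, for a purpose that they cannot serve.

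**Conclusion.** The concern holds as a minor one. The Yates chi-square on presenting severity does not match how severity is recorded and lacks a cut-point; under the assumptions above, the choice among four cuts changes the verdict in about 8% of trials. The t-test on race is uninterpretable if race has three or more categories. Neither test can establish that the arms are similar.

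A reader might infer that the primary result is compromised, or that a 60-min comparison not adjusted for baseline is biased. The documents support neither. Nothing in the plan depends on the baseline tests. Under randomisation the unadjusted comparison is unbiased, and its standard error already allows for chance imbalance at baseline. Adjustment offers precision only: a half-width of 16.9 to 12.6 mm instead of 17.6 mm, for an assumed correlation of 0.3 to 0.7, an implied SD of about 35 mm and 32 per arm.

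**What to change.** **Correction (section 6.3, baseline sentence).** Replace it with: Baseline characteristics will be summarised by arm, with age and presenting headache VAS as mean (SD) and gender and race as n (%); no significance test will be used to judge similarity. If tests are kept, use t-tests for age and presenting VAS, and chi-square or Fisher's exact tests for gender and race. Cost: one rewritten sentence.

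**Optional improvement, independent of the correction.** State in section 6.3 that the primary estimate is the between-arm difference in headache VAS at 60 min, from a repeated measures model with the 15, 30, 45 and 60-min values as outcomes and the pre-treatment VAS as a covariate with its own slope at each time, whatever balance is observed. Use the same definition in sections 6.1 and 3.6.1. Cost: one sentence and matching words in two places. No new data are needed, because the pre-treatment VAS is already collected at Visit 1.

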#### 3.2. Hypotheses, Research Questions or Objectives:

We will determine the difference in pain scores between the compazine and Ketamine groups, as measured by a 25-mm difference between the groups mean on the visual analogue scale (VAS) at 60 min.

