Ketamine or compazine) and "randomized add-on medication" (for the ondansetron (Zofran) or diphenhydramine (Benadryl)). It is common practice to use the combination of compazine and diphenhydramine (Benadryl) or ketamine and ondansetron (Zofran). If the patient receives a rescue medication, he or she will definitely NOT be withdrawn from the study. The need for rescue medication is a secondary outcome of the study. We will still analyze groups based upon their original randomization and the intention to treat principle. Rescue medications do not bias the study results, and they have been part of every headache treatment study I have ever read. The data from the first 30-minutes will be maintained as research data, and this is important data for the study.

**Safety:** After 30 minutes, the treating provider will be permitted to administer any medication they would like for further treatment. Only if there is an untoward event that requires the treating provider to know which medication was administered will the pharmacist unblind the randomization for that individual patient.

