#### 6.1. Outcome Measures:

The primary outcome measure will be the difference in pain scores between the compazine and Ketamine groups, measured as the absolute difference between the means at 60 min. Secondarily, we will measure the difference between the rates of decline in pain scores, rate of admission, nausea scores, rate of vomiting, rate of development of akathisia, heart rate and blood pressure changes, headache resolution with telephone follow up, and patient satisfaction.

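### Section 6.3 names no test, estimate or confidence interval for the 60-minute difference in mean VAS; its repeated-measures ANOVA has no stated decisive effect, so the 80% power is not tied to the planned analysis

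*Combined protocol and SAP*

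**What the plan says.** Section 3.2 states the objective as a difference in pain scores, "as measured by a 25-mm difference between the groups mean on the visual analogue scale (VAS) at 60 min". Section 6.1 defines the primary outcome as the group difference in pain scores, "measured as the absolute difference between the means at 60 min"; section 3.6.1 has the same definition. Section 6.1 then lists "the difference between the rates of decline in pain scores" among the secondary measures. Section 6.2 sizes the trial on the same quantity: "Thirty-two patients will be needed in each group to find a 25-mm difference between the group means on the VAS at 60 min", with power 0.80 and alpha 0.05. It gives no SD, sidedness or test.

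Section 6.3 has two sentences. The first concerns baseline comparability only: a t-test for gender, race and age, and a chi-square "test with Yates correction on severity of presenting headache, to determine if they are similar". The second is the whole of the outcome analysis: "The individual VAS measurements will be compared using a repeated measures analysis of variance (ANOVA) test".

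Headache VAS is recorded before treatment (section 3.6, Visit 1: "Headache severity via 100-mm VAS") and at 15, 30, 45 and 60 minutes. The Safety paragraph of section 3.6 adds: "After 30 minutes, the treating provider will be permitted to administer any medication they would like for further treatment". Section 3.6 also commits to analysis as randomised.

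**The concern.** A repeated-measures ANOVA with a group factor and a time factor yields two between-group tests. The group effect compares averages over all included times. The group-by-time effect asks whether the two curves have different shapes, which is close to the rate-of-decline question that section 6.1 makes secondary. Neither estimates the difference at 60 minutes. Section 6.3 does not say which effect decides the trial or whether the baseline score is one of the time levels. That leaves at least four candidate tests, none of which is the comparison that was powered.

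Two things are at stake. If the deciding effect is chosen after the data are seen, the type I error exceeds 0.05. And an ANOVA effect can be significant because of early differences alone. That would be a real difference between curves and not a false positive, but it would not answer the 60-minute question. Because further medication is allowed after 30 minutes, curves that separate early and meet by 60 minutes could occur here.

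A lesser point: section 6.3 uses baseline headache severity only in a similarity check. Leaving it out of the outcome model loses precision but does not cause bias.

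**Working it through.** **1. The plan's own figure.** The 32 per group cannot be reproduced directly, because no SD is given, but the implied SD can be recovered. Inputs from section 6.2: n = 32 per group, difference 25 mm, power 0.80, alpha 0.05. Assumed: two-sided, two-sample comparison of means.

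- Normal approximation: SD = 25 × √(32/2) / (1.960 + 0.842) = 100 / 2.802 = 35.7 mm.
- Noncentral t, 62 df: standardised difference 0.711, so SD = 25 / 0.711 = 35.1 mm.

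So 32 per group fits a t-test at 60 minutes with SD about 35 mm. (One-sided, the implied SD would be about 40 mm.)

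**2. Power of the ANOVA effects.** Assumptions beyond the documents: SD 35.1 mm at every time, equal within-patient correlation ρ from 0.3 to 0.7, and the trajectories below. T = 5 times with baseline as a level, T = 4 without. Let d_t be the group difference at time t and d̄ its mean over the included times.

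- Group effect: noncentrality = (n/2) d̄² / [SD² (1 + (T−1)ρ)/T], F on 1 and 62 df.
- Group-by-time: noncentrality = (n/2) Σ(d_t − d̄)² / [SD² (1 − ρ)], F on T−1 and 62(T−1) df.

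Worked case: linear growth, T = 5, ρ = 0.5. The differences are 0, 6.25, 12.5, 18.75 and 25 mm, so d̄ = 12.5 and Σ(d_t − d̄)² = 390.6. With SD² = 1234.7:

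- Group: 16 × 156.25 / (1234.7 × 0.6) = 3.37; power 0.44.
- Group-by-time: 16 × 390.6 / (1234.7 × 0.5) = 10.12; power 0.71.

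Across ρ = 0.3 to 0.7, with a true 25-mm difference at 60 minutes in each row (60-minute t-test power 0.80 throughout):

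| Difference over time | Group, baseline in | Group-by-time, baseline in | Group, baseline out | Group-by-time, baseline out |
|---|---|---|---|---|
| Grows linearly to 25 mm | 0.36–0.56 | 0.55–0.92 | 0.51–0.72 | 0.32–0.67 |
| 25 mm constant from 15 min | 0.73–0.92 | 0.67–0.97 | 0.89–0.98 | 0.05 |
| 25 mm at 60 min only | 0.10–0.14 | 0.67–0.97 | 0.13–0.17 | 0.68–0.97 |

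**3. No difference at 60 minutes.** With differences of 25, 20, 10 and 0 mm at 15, 30, 45 and 60 minutes, group-by-time is significant in 0.69–0.98 of trials with baseline in and 0.57–0.93 with it out. A 60-minute test is significant in 0.05.

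**4. Flexibility (simulation, 20,000 trials per setting).** With no true difference at any time, success on either the group or the group-by-time effect (baseline in) has probability about 0.09–0.10; success on any of the four readings, about 0.12. In the linear case with baseline in, the two effects disagree on significance in about 50% to 62% of trials.

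**5. A 60-minute ANCOVA on baseline.** Residual SD = SD × √(1 − r²), where r is the baseline-to-60-minute correlation; 61 df. For example, r = 0.5 gives 35.1 × 0.866 = 30.4 mm.

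| r | Power | 95% CI half-width (mm) |
|---|---|---|
| unadjusted | 0.80 | 17.6 |
| 0.24 | 0.82 | 17.1 |
| 0.3 | 0.84 | 16.8 |
| 0.5 | 0.90 | 15.2 |
| 0.7 | 0.98 | 12.5 |

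**The case against.** The best defence is that the plan fixes more than section 6.3 suggests. The outcome, time point, 25-mm benchmark and analysis by randomised group are all stated. Comparing the individual measurements could mean comparing the groups at each time within the repeated-measures model, with 60 minutes primary because section 6.1 says so. Since rate of decline is listed as secondary, group-by-time was probably not meant to decide the trial. On that reading one sentence is missing, and the inflated type I error needs an analyst who ignores section 6.1.

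Part of this stands. The effect measure is defined; what is absent is the test, estimator and interval for it. A 60-minute contrast can be taken from such a model and would answer the question. The type I figures are conditional: 0.12 describes success on any of four readings, not an expected error rate. The power figures rest on assumed trajectories and correlations and on a back-solved SD. An unadjusted 60-minute comparison would also close the gap, so covariate adjustment is an improvement and not a necessity.

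It does not remove the problem. The favourable reading has to be supplied by the reader: section 6.3 names a t-test, but only for baseline characteristics, and no other section states a 60-minute contrast.

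**Conclusion.** The concern holds and should be corrected before outcomes are compared by group. The analysis named in section 6.3 does not, as written, test the comparison defined in section 6.1 and powered in section 6.2, so the stated 0.80 does not carry over to it. This follows from the text alone.

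The calculations show that it matters. With the same 25-mm difference at 60 minutes, power ranges from 0.05 to 0.98 depending on the effect, the handling of baseline and the trajectory. ANOVA power can therefore be far below, equal to or above 0.80. These are illustrations under an implied SD of 35.1 mm and equal correlations of 0.3 to 0.7, not estimates of this trial's actual power.

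**What to change.** Name one primary analysis in section 6.3. Suggested text:

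> Primary analysis: headache VAS at 60 minutes, compared between groups as randomised by ANCOVA with treatment group as factor and baseline headache VAS as covariate; two-sided alpha 0.05; adjusted mean difference with 95% confidence interval.

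A mixed model of the post-baseline scores, with baseline as covariate and a prespecified 60-minute contrast, is an acceptable alternative and keeps subjects who miss a time point. Either way, report by arm how many subjects lack a 60-minute score. Keep the repeated-measures analysis as secondary, for the rate-of-decline question.

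The cost is a wording change. Baseline VAS is already collected, no patients or visits are added, and the covariate uses one residual degree of freedom (62 to 61). With 32 per group, power stays at about 0.80 or more if the SD is about 35 mm or less, as the plan's own sample size implies; at SD 40 mm an unadjusted 60-minute test would have 0.69. The gain from adjustment is small if baseline and 60-minute scores are weakly correlated.

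### Section 6.3 names only a repeated measures ANOVA for the VAS: in standard form it discards patients with one missed reading, has no term for the primary 60-min difference, and leaves sphericity open

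*Combined protocol and SAP*

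**What the plan says.** Section 6.3 gives the whole analysis of the pain scores in one sentence: "The individual VAS measurements will be compared using a repeated measures analysis of variance (ANOVA) test". It names no model terms, covariance structure, sphericity check or rule for missing readings, and no other section supplies them.

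Section 6.1 makes the between-arm difference in mean pain score at 60 min the primary outcome. Among the secondary outcomes it lists "the difference between the rates of decline in pain scores", with no test assigned to it. The visit lists in section 3.6 and the count in section 3.6.5 give five headache VAS readings per patient: Visit 1, then 15, 30, 45 and 60 min after treatment.

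On numbers, section 6.2 says "Thirty-two patients will be needed in each group to find a 25-mm difference between the group means on the VAS at 60 min". It sets 80% power and a 5% alpha, and adds: "We will aim for 35 patients per group to account for about a 10% dropout rate". Section 6.4 plans 70 enrolled and 64 completing. In section 3.6, the text on dose administration says: "We will still analyze groups based upon their original randomization and the intention to treat principle". That sentence follows directly on statements that patients given rescue medication stay in the study.

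**The concern.** Three things follow from naming this method and nothing more.

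First, the standard repeated measures ANOVA needs a complete row for each patient. One missed reading removes the patient, even when the 60-min score that defines the primary outcome was obtained. This sits poorly with an analysis of patients as randomised.

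Second, the primary outcome is a contrast at one time point, while the ANOVA yields a group effect averaged over all readings, a time effect and a group-by-time interaction. None of these is the 60-min difference, so the plan does not say how the primary estimate will be obtained.

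Third, readings 15 minutes apart are likely to correlate more strongly when adjacent than when distant. Sphericity then fails, and the uncorrected group-by-time test rejects too often. That term is the natural candidate for the outcome on speed of decline.

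At stake are avoidable loss of patients from the primary comparison, a primary estimate left open until the data are in, and an excess of false positives on one secondary outcome.

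**Working it through.** **The plan's own figure.** Section 6.2 gives 32 per arm for 25 mm but no SD. Solving n = 2(1.96 + 0.84)² SD² / 25² for n = 32 gives SD ≈ 35.7 mm (35.1 mm with the t distribution). The 32 therefore cannot be reproduced independently; it implies an SD of 35 to 36 mm. For dropout, 32/0.9 = 35.6, or 36 rounded up, against the stated 35, a trivial difference. Section 6.4 implies 1 − 64/70 = 8.6% loss.

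**Patients lost to incomplete rows.** The documents give no missingness rate per reading. Let m be the assumed probability that any one reading is missing, independently of the others. The share lost is 1 − (1 − m)⁵. The share lost although the 60-min score exists is (1 − m)[1 − (1 − m)⁴].

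- m = 2%: 1 − 0.98⁵ = 9.6% lost, about 63 of 70 left. Of the loss, 0.98 × 7.8% = 7.6% (about 5 patients) have a 60-min score.
- m = 3%: 1 − 0.97⁵ = 14.1% lost, about 60 left. Of the loss, 0.97 × 11.5% = 11.1% (about 8 patients) have a 60-min score.
- m = 5% and 10%: about 54 and 41 left.

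The plan needs 64. With 30 per arm and the implied SD of 35.7 mm, 25 / (35.7 × √(2/30)) = 2.71 and 2.71 − 1.96 = 0.75, so power is about 77% instead of 80%.

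**What the ANOVA terms estimate.** Suppose the gap between arms opens in a straight line from 0 at baseline to 25 mm at 60 min. The five gaps are 0, 6.25, 12.5, 18.75 and 25 mm, and the group main effect averages them to 62.5/5 = 12.5 mm, half the primary difference. The interaction is a joint test on 4 degrees of freedom and gives no single estimate.

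**Type I error of the group-by-time test.** The check used 40,000 simulated trials per setting, with no true difference, 32 per arm, five readings and a nominal 5%. The correlation structures are assumed, because the documents give none.

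| Assumed structure | Uncorrected | Greenhouse-Geisser |
|---|---|---|
| Compound symmetry | 4.9% | 4.5% |
| AR(1), 0.5 | 6.2% | 4.7% |
| AR(1), 0.7 | 7.0% | 4.8% |
| AR(1), 0.8 | 7.6% | 4.8% |
| AR(1), 0.9 | 8.0% | 4.9% |
| Baseline correlated 0.3, other readings 0.8 | 8.0% | 5.0% |
| Random slope | 8.8% | 4.9% |

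With the four post-dose readings only, AR(1) of 0.5 to 0.9 gives 5.8% to 7.0% uncorrected. The group main effect stays at 4.8% to 5.0% throughout. A comparison at the single 60-min time point does not depend on sphericity.

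**The case against.** The strongest reply is that section 6.3 is brief, not wrong. It does not say that incomplete patients will be excluded or that no correction will be applied, and a competent analyst could do both properly. That is fair: on both matters the plan is silent.

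A reader might infer that the plan contradicts its own intention-to-treat statement. The documents do not support that. The sentence in section 3.6 concerns patients who receive rescue medication and is not a rule for missing readings. The tension is one of spirit.

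A reader might also infer that the test of decline runs at 8%. That is one result among several and needs strong serial correlation or a weakly related baseline. The link from that outcome to the group-by-time term is also inferred, because section 6.1 assigns no test.

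The 2% to 3% missingness is likewise assumed, and the resulting loss lies near what the sample size already allows for. Patients who leave early have no 60-min score to discard, so the avoidable loss comes only from gaps before 60 min. Nothing in the documents says which patients would miss readings, so no direction of bias can be claimed.

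What the reply does not answer is that this is the only method named for the pain scores, and that no term of it is the primary estimate. Left as it is, the choices on missing data, correction and contrast can be made after the data are seen.

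**Conclusion.** The point holds as a weakness in the choice and specification of the method, one that should be put right and is cheap to put right. In its standard form, the named ANOVA would lose about 10% to 14% of patients at an assumed 2% to 3% independent missingness per reading, against about 10% budgeted. Roughly 5 to 8 of 70 patients would be dropped despite having a 60-min score. The cost in power is small at those rates and grows if missingness is higher. No ANOVA term directly estimates the primary 60-min difference.

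An uncorrected group-by-time test would have a type I error of about 5% to 9%: 5% under compound symmetry and about 6% to 8% for AR(1) correlations of 0.5 to 0.9. This concerns a secondary outcome only. It would be wrong to conclude that the primary 60-min comparison has an inflated error rate.

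**What to change.** Replace the sentence in section 6.3 with a mixed model for repeated measures on all available VAS readings, with unstructured covariance and adjustment for baseline VAS. Pre-specify the 60-min arm contrast as the primary estimate, with its confidence interval. With about 32 patients per arm, name a small-sample degrees-of-freedom method such as Kenward-Roger.

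Test the speed of decline with a contrast that includes the change from baseline. One way is to keep baseline as a response, constrain the arm means to be equal there, and test the arm-by-time terms at 15, 30, 45 and 60 min jointly. An arm-by-time term on post-dose readings alone will not do: if one arm falls faster before 15 min and the gap then stays constant, that term is zero and the difference is missed.

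If ANOVA is kept for the secondary scores, apply the Greenhouse-Geisser correction and state how missing readings are handled.

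The mixed model assumes that data are missing at random, and it recovers no information on patients without any post-dose reading. Add a simple sensitivity analysis, for example one that shifts imputed 60-min scores over a stated range in each arm. The cost is SAP wording and a little analysis time, with standard software and no new data or visits.
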